Only a large multicentre RCT can address whether the age of RBC transfusion affects mortality. Accordingly the TRANSFUSE study will have important health policy implications regardless of the outcome, in Australia and internationally.

OBJECTIVES

Aim

This study aims to determine whether, compared to standard care, transfusion of the freshest available allogeneic RBC decreases mortality of patients admitted to ICU.

Hypothesis

In critically ill patients who require a RBC transfusion, compared to standard practice, the administration of the freshest available compatible RBC reduces 90-day patient mortality.

STUDY OUTCOME MEASURES

Primary outcome

90 day mortality

Secondary outcomes

1. 28 day mortality
2. Persistent Organ Dysfunction combined with death at 28 [47]
3. Days alive and free of mechanical ventilation at day 28 post randomisation
4. Day alive and free of renal replacement therapy at day 28 post randomisation
5. Blood stream infection in ICU (post randomisation)
6. Length of stay in ICU and in hospital post randomisation
7. Proportion of patients who suffer at least one febrile non-haemolytic transfusion reaction in ICU
8. EQ-5D score at day 180 post randomisation [48]

OVERALL STUDY DESIGN

Study design

TRANSFUSE-RCT is a multi-centre, randomised, double blind, controlled trial, testing the effect of the freshest available RBC compared to standard practice, on mortality in critically ill patients who require RBC transfusion.

Study treatments

- Freshest available blood group: These patients will receive the freshest available group-specific compatible RBC unit in the transfusion service.
- Standard care group: These patients will receive standard practice, which is the oldest available group-specific compatible RBC unit in the transfusion service.

Study population

ICU patients or emergency department patients accepted for ICU admission in participating hospitals who meet all inclusion criteria and have no exclusion criteria. The study will enrol 5000 patients, in approximately 50 centres in Australia and New Zealand (ANZ).

Our observational study indicated that the recruitment of 40 patients per week is feasible and conservative [3]. At such a rate study recruitment would be completed in approximately 2.5 years. Allowing for study set up (12 months), 90 day outcome assessments, monitoring and analysis, a study time period of 4 years is anticipated.

Inclusion criteria

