ICU patients* with an anticipated ICU stay of at least 24 hours, in whom the decision has been made by medical staff to transfuse at least one RBC unit.

*A patient can be included into the study in the Emergency Department if the decision to admit the patient into the ICU has been taken.

Exclusion criteria

- Age younger than 18
- Previous RBC transfusion during the current hospital admission (including transfusion in another hospital for transferred patients)
- Diagnosis of transplantation or hematologic malignancy
- Pregnancy
- Cardiac surgery during the present hospital admission
- Expected to die imminently (<24hrs)
- The treating physician believes it is not in the best interest of the patient to be randomised in this trial.
- Known objection to the administration of human blood products
- Participation in a competing study (see below)

Co-enrolment

- Co-enrolment into any RBC transfusion studies is not permitted
- TRANSFUSE patients cannot be co-enrolled into the POLAR, ARISE, TRISS, and IRONMAN studies.
- Co-enrolment in the ADRENAL, EPO-TBI, PHARLAP, and SPICE studies is permitted by the TRANSFUSE management committee
- Co-enrolment in single site studies is permitted (excluding blood transfusion studies)

STUDY PROCEDURES

Eligible patients

Patients will be screened in the ICU and emergency department for their potential eligibility by the ICU research coordinator (RC) and clinicians. The ICU RC will place a sticker on the patient's chart to assist the ICU team with identifying eligible patients when a blood transfusion is ordered.

Enrolment

The inclusion and exclusion criteria will be checked when a clinical decision is made to transfuse. Transfusion indication, timing and number of the RBC units will be determined by the treating clinicians. However, we recommend following the current ANZ transfusion guidelines for ICU patients [49].

Randomisation

Randomisation will be performed by the ICU research staff using a Web-based computer system.

The patient will be allocated a unique study identification number at randomisation to identify their study involvement for the first and each subsequent RBC transfusion during their hospital stay. This number will be recorded on a sticker placed in the patient's chart and also on the RBC request form sent to the hospital transfusion service. The treatment allocation will be determined using variable block randomisation in a 1:1 ratio, stratified by centre.

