We estimated the baseline mortality using the prospective ANZ observational study data [3]. Over 5 weeks in 2008, 757 patients were recruited. The exclusion criteria of TRANSFUSE leaves 45% recruitable patients. These patients had a hospital mortality of 25% and we conservatively estimate 90-day mortality to be 28%. Our sample size calculation is based on a 15% relative decrease in 90-day mortality, or an absolute decrease of 4.2% from 28% to 23.8%. This effect size would be clinically highly relevant (Number needed to treat to save one life [NNT]=24). This relative decrease is much less than observed in the Koch study (30% RRR) [28], and in our observational study where we found a mortality of 21.3% in the older three quartile versus 13.2% in the freshest quartile (38% RRR) [3]. With a type I error of 0.05 and a type II error of 0.1 (power 90%), the required patient number is 2332 per group. According to our previous studies [54, 55], loss to follow up should not exceed 5%, giving an accurate number of 4898 patients which has been rounded up to 5000 patients.

Statistical and analytical plan

This study will be analysed on an intention-to-treat basis. Analysis will primarily be conducted using SAS version 9.2. (SAS Institute Inc., Cary, NC USA). Baseline comparisons will be performed using chi-square tests for equal proportion, student t-tests for continuously normally distributed variables and Wilcoxon rank sum tests otherwise. The primary outcome, 90 day all-cause mortality will be analysed using a Chi-square test statistic, with results reported as frequencies and percentages per arm. Adjustment for strata (centre) will be made using logistic regression for binomial outcomes and Cox Proportional Hazards regression for time to event data with results reported as Odds Ratios (95% CI) or Hazard ratios (95% CI) respectively. In the unlikely event that baseline imbalances are found to exist between treatment groups, sensitivity analysis will be performed with imbalanced variables included as covariates. A two-sided p-value of 0.05 will be considered to be statistically significant. Additionally a per protocol analysis will be undertaken to account for patients with alloantibodies for whom freshest blood is unavailable. A detailed statistical analysis plan will be published prior to analysis being performed.

Subgroup analyses

A priori subgroup analyses will include:

- Group O versus non group O
- Illness severity according to APACHE III and SOFA scores

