Patient and transfusion data: will be routinely collected as part of the data collected for the TRANSFUSE-trial. Dates and times when samples are taken and results of the experiments performed in the study sites will be recorded in a separate case report form (CRF).

Blood samples: Blood samples (2 x5 ml in lithium heparin tube, 1 x K2E 3ml EDTA (lilac top) tube and 1 x 5 ml in gel lithium heparin) will be sent immediately to the pathology lab of each hospital where plasma samples will be aliquoted and stored at - 80°C before transfer to the Australian Red Cross Blood Service Melbourne Processing Centre (MPC), where they will be stored until recruitment is complete and experiments are performed. For further details refer to the section below “blood sample schedule.”

Experiments:

- Bilirubin, free haemoglobin, haptoglobin, ferritin, serum iron, transferrin and transferrin saturation will be performed in each pathology laboratory at the 3 participating centres.
- The other experiments will be performed at a later date once all patients have been enrolled and samples collected. These experiments are outlined below:
 - i) Non transferrin bound iron (NTBI) and labile plasma iron (LPI, a fraction of NTBI that is redox active) will be measured by FeROS eLPI and LPI assays (Aferrix, Israel), and serum hepcidin will be measured using a commercially available ELISA (DRG, Germany).
 - ii) Bacterial growth will be performed in plasma before and after transfusion without and with desferrioxamine as described elsewhere [64].
 - iii) Inflammatory biomarkers: sCD106 (VCAM-1), sCD62L, sCD62P, ICAM-1, MCP-1, MIP-1a, MIP-1 β , IL-1 α , IP-10, IL-6, IL-8, IL-10, IL-12, IL-4, IL-13, IL-17, IL-21, IFN- γ and IFN- α , will be assessed in plasma samples via multiplex Cytometric Bead Array (BD Biosciences).
 - iv) Leucocyte adhesion

Blood samples schedule

Samples will be taken within 1 hour prior to transfusion (T0), 4 hours after transfusion initiation (T4) and 24 hours after transfusion initiation. For example, if the first RBC transfusion starts at 10 am, the samples T0 will be taken between 9 am and 9.59 am, at 2 pm (samples T4) and at 10 am the following day (samples T24).

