Statistical analysis: Data collected for the sub-study will be treated and analysed separately after the TRANSFUSE RCT has been completed. Data will be transformed when skewed and analysis performed on log-transformed values. Parameters before and after the transfusion episode will be compared for each patient using paired t-test. Biological parameters post-transfusion, as well as differences between pre- and post-transfusion values, will be compared according to RBC storage duration category, which will be defined according to the RCT (i.e.: freshest available vs. standard issue) and also according to whether patients were transfused with only RBC younger than 14 days vs. patients transfused with RBC older than 14 days. A correlation between patient severity at randomisation and each parameter (including: post-transfusion extravascular haemolysis and NTBI) will also be performed. A sub group analysis will be performed on the most severe patients according to their SOFA score on the day of transfusion.

Safety

As per the TRANSFUSE trial. There are no additional risks posed by the IT TRANSFUSE sub-study. The results of the study will be forwarded to the Data and Safety Monitoring Committee (DSMC).

Funding

This study is collaboration with the Australian Red Cross Blood Service, who has provided funding for the costs for research staff time, sample collection, processing and testing in addition to in kind support provided by the Blood Service.

Publication

The study will be conducted in the name of Monash University on behalf of the TRANSFUSE investigators. Authorship will be under the names of the sub-study investigators on behalf of the TRANSFUSE investigators. Publication of results will be embargoed until publication of the main study results unless specific permission for early publication is given by the TRANSFUSE management committee.

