- b) The proportion of patients requiring ongoing renal replacement therapy at 90 day follow-up

- c) The severity of AKI measured as the change in serum creatinine from baseline (continuous variable)
- d) The duration of AKI measured as AKI free days (number of days not in stage 1-3 categories) for ICU stay
- e) Comparison of the mean creatinine levels across the first 28 days

The fact that we are including several outcomes related to renal function will allow this study to provide a more comprehensive picture of the impact of RBC storage duration on renal function and will increase the possibility of detecting an effect if there is one.

Power calculations and sample size

This substudy will analyse data for 2000 patients. With 1000 patients per group, we will have an 80% power (2 sided p-value of 0.05) to show a difference of 5.3% (19.5% vs 24.8%) of AKI any stage. This is taken from a recent article reporting an incidence of AKI (defined by the RIFLE criteria) of 24.8% in anaemic transfused ICU patients compared to 16.7 % in anaemic non transfused ICU patients ($p < 0.05$)[73]. If the harmful effect of blood is mainly due to storage duration[73] a sample size of 550 patients per group would be enough to detect a difference of this magnitude (8.1%, 16.7% v. 24.8%). However, we don't exclude that fresh RBC may also be deleterious to a degree, therefore, we have decided on a more conservative approach with a sample size of 1000 patients per group.

Alternatively, stage 3 AKI (KDIGO criteria) is the most severe stage of AKI and therefore the category in which we are most likely to detect a difference between groups. With 1000 patients per group we will have more than enough power to detect a difference of 10.2% (11.2% vs 21.4%) in stage 3 AKI[70].

Statistical Analysis

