Data will be assessed for normality and log-transformed where appropriate. Univariate analysis will be conducted using student t-tests, chi-square test for equal proportion or non-parametric tests where appropriate. Multivariate analysis will be performed adjusting for baseline imbalances and known covariates and confounders. Multiple logistic regression will be used for AKI as a binomial outcome. Linear regression will be used for analysis of continuous outcomes. The difference between groups for daily serum creatinine will be determined using generalised linear modelling fitting main effect for group and time and an interaction between group and time to determine if the two groups behave differently over time. A two-sided p-value of 0.05 will be considered to be statistically significant. All data will be analysed using Intercooled Stata, version 9 and above (Statacorp, College Station, Tx, USA).

Publication

The study will be conducted in the name of Monash University on behalf of the TRANSFUSE investigators. Authorship will be under the names of the sub-study investigators on behalf of the TRANSFUSE investigators. Publication of results will be embargoed until publication of the main study results unless specific permission for early publication is given by the TRANSFUSE management committee.

REFERENCES

1. Corwin, H.L., et al., *The CRIT Study: Anemia and blood transfusion in the critically ill--current clinical practice in the United States*. Crit Care Med, 2004. **32**(1): p. 39-52.
2. Vincent, J.L., et al., *Anemia and blood transfusion in critically ill patients*. Jama, 2002. **288**(12): p. 1499-507.
3. Pettila, V., et al., *Age of red blood cells and mortality in the critically ill*. Crit Care, 2011. **15**(2): p. R116.
4. Investigators, T.B.O.S., *Transfusion practice and guidelines in Australian and New Zealand intensive care units*. Intensive Care Med, 2010. **36**: p. 1138-1146.
5. Service, A.R.C.B., *Annual Report*, h.w.d.c.a.f.p.B.S.a. report, Editor 2007 to 2010.
6. Hebert, P.C., et al., *A multicenter, randomized, controlled clinical trial of transfusion requirements in critical care*. Transfusion Requirements in Critical Care Investigators, Canadian Critical Care Trials Group. N Engl J Med, 1999. **340**(6): p. 409-17.
7. Marik, P.E. and H.L. Corwin, *Efficacy of red blood cell transfusion in the critically ill: a systematic review of the literature*. Crit Care Med, 2008. **36**(9): p. 2667-74.

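### Centre, the randomisation stratum, is not named in either substudy's analysis; adding it costs nothing and recovers about 0 to 3 points of power

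*Combined protocol and SAP*

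**What the plan says.** The Randomisation section states: "The treatment allocation will be determined using variable block randomisation in a 1:1 ratio, stratified by centre". The main Statistical and analytical plan follows through: "Adjustment for strata (centre) will be made using logistic regression for binomial outcomes", with Cox regression for time-to-event data.

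Each substudy has its own statistical section, and neither names centre.

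- **Renal substudy (Appendix 4, Statistical Analysis).** "Univariate analysis will be conducted using student t-tests, chi-square test for equal proportion or non-parametric tests where appropriate". Multivariable logistic and linear models follow, adjusting for baseline imbalances and for known covariates and confounders that are not listed. The daily creatinine model does list its terms: group, time and their interaction.
- **Iron substudy (Appendix 3, Statistical analysis).** "Biological parameters post-transfusion, as well as differences between pre- and post-transfusion values, will be compared according to RBC storage duration category". The categories are the randomised arms and, separately, whether all units were younger than 14 days. The only named test is a paired t-test for within-patient change; no between-group test is specified. The data are to be analysed separately from the main trial.

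In the iron substudy, bilirubin, free haemoglobin, haptoglobin, ferritin, serum iron, transferrin and transferrin saturation "will be performed in each pathology laboratory at the 3 participating centres". Non-transferrin bound iron (NTBI), labile plasma iron (LPI), hepcidin, bacterial growth and cytokines are assayed later on stored samples gathered at one processing centre. The primary outcome draws on both sets.

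**The concern.** Stratified blocks balance the arms within each centre, so centre differences largely cancel from the treatment contrast. A test that ignores centre still counts those differences as noise. It overstates the standard error, so intervals are too wide, type I error falls below its nominal level and some power is lost.

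In the iron substudy, centre is also the laboratory for the routinely measured indices, so calibration differences add to patient differences. In the renal substudy, creatinine comes from routine values at many hospitals, and the secondary outcome comparing mean creatinine levels does not remove additive differences between sites.

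**Working it through.** **1. The plan's own sizes.** Renal: 19.5% v 24.8%, two-sided 0.05, 80% power. With pooled proportion 0.2215,

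n = [1.96√(2×0.2215×0.7785) + 0.8416√(0.195×0.805 + 0.248×0.752)]² / 0.053² = 963 per group,

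and 1000 with continuity correction, which matches the plan. Power at 1000 per group without the correction is 81.5%.

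Iron: difference 2.2, SD 3.7. n = 2(1.96+1.2816)²(3.7/2.2)² = 59.4, so 60 per arm. Then 120/(1−0.20) = 150, which matches. Power is not stated; 90% is inferred because 80% would give 113.

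**2. Formula.** Let ρ be the share of total variance that lies between centres, with arms balanced within each centre. The unstratified test uses SE = σ√(2/n), but the true standard error is SE√(1−ρ). Hence:

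- type I error = 2[1−Φ(1.96/√(1−ρ))]
- power without centre = Φ((δ−1.96 SE)/(SE√(1−ρ)))
- power with centre = Φ(δ/(SE√(1−ρ)) − 1.96)

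**3. Iron, locally measured indices.** The documents give no effect or SD for these, so the standardised effect planned for NTBI is borrowed for illustration: SE = 3.7√(2/60) = 0.6755 and δ/SE = 3.257. Total SD is held at 3.7; ρ is assumed.

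| ρ | Type I, no centre | Power, no centre | Power, with centre | Loss (points) |
|---|---|---|---|---|
| 0.05 | 4.4% | 90.8% | 91.6% | 0.8 |
| 0.10 | 3.9% | 91.4% | 93.0% | 1.5 |
| 0.20 | 2.8% | 92.6% | 95.4% | 2.7 |

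Simulation with three sites of 40 and permuted blocks of 2, 4 or 6 (assumed) gave losses of 1.0, 1.3 and 2.9 points.

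**4. Balance.** The type I figures need intact within-site balance. The iron substudy takes only some of each site's randomised patients (separate consent, working hours, an extra exclusion, incomplete data). At ρ = 0.20, simulated type I error was 2.7% with intact blocks, 4.0% when one third of each site's patients were sampled, and about 5% when balance was lost.

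**5. Renal.** The number of participating centres is not given. The simulation used 50 centres of 40 (the main protocol expects about 50 centres), blocks as above and the plan's rates, with 6000 runs per cell. It compared chi-square with a Cochran-Mantel-Haenszel (CMH) test by centre.

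| Assumed ICC | Type I, chi-square / CMH | Power, chi-square / CMH | Loss (points) |
|---|---|---|---|
| 0.01 | 5.1% / 5.2% | 80.6% / 80.7% | 0.1 |
| 0.04 | 4.0% / 4.4% | 83.0% / 84.0% | 1.0 |
| 0.09 | 4.4% / 5.2% | 83.0% / 84.8% | 1.8 |
| 0.15 | 3.2% / 4.9% | 83.7% / 86.9% | 3.2 |

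Monte Carlo error is about 0.3 points on type I error and 0.5 on power.

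**6. Reach of the laboratory argument.** It covers post-transfusion values of the indices run in the hospital laboratories. It does not cover NTBI, which sizes the substudy, or LPI. Pre/post differences remove additive offsets; on the log scale, which is planned for skewed data, they also remove proportional ones.

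**7. The 14-day comparison.** Patients are grouped by the blood they received, not by allocation. If sites differ in the age of their stock, site is related both to the grouping and, through the laboratory, to the outcome. The formula in step 2 does not apply, and the error can go either way.

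**The case against.** The strongest reply is that silence is not a decision to leave centre out. The renal models adjust for known covariates, which could include centre, and the iron plan names no between-group test at all. A reader might infer that both substudies have chosen to ignore centre; the documents support only that centre is not named. What stands is that the renal univariate tests as written have no stratum, and the creatinine model lists its terms without centre. The iron data are analysed separately, so adjustment cannot be assumed to carry over from the main plan.

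A second reply is that the effect is small, in the safe direction, and partly removed by the planned pre/post differences. That is right for the randomised comparisons.

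A reader might also infer that the iron substudy is underpowered. Treating 3.7 as the within-laboratory SD and adding offsets on top gives Φ(3.257−1.96√1.25) = 86% when the offset SD is half of 3.7, and Φ(3.257−1.96√2) = 69% when they are equal. The documents do not support this. The effect of 2.2 belongs to NTBI, which the hospital laboratories do not measure. Nothing says 3.7 excludes between-laboratory variation, and no offset of that size is reported.

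**Conclusion.** The point holds as a free improvement. Centre is a stratification factor that the main analysis adjusts for, and neither substudy names it. For randomised, unadjusted comparisons the cost is slightly wide intervals and about 0 to 3 points of power. In the renal substudy this is 0 to 2 points for ICC up to about 0.09 and about 3 at 0.15. For post-transfusion values of the locally measured iron indices it is about 1 to 3 points for a laboratory share of 5 to 20%. Centre variance, block sizes and equal centre sizes are all assumed, and the iron effect size is illustrative.

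Power stays above the renal plan's stated target ("With 1000 patients per group, we will have an 80% power (2 sided p-value of 0.05") and above the 90% inferred for iron in every scenario tabulated, so no shortfall is shown. It would also go too far to call all the substudy tests conservative. Type I error is 4.4% to 2.8% in the iron case only with intact balance, and closer to 5% once sampling breaks the blocks. The 14-day comparison is not randomised, so its possible bias has no known direction.

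**What to change.** **Appendix 4, Statistical Analysis.** Include centre in the logistic models for any AKI and stage 3 AKI, or use a Cochran-Mantel-Haenszel test by centre. Include it also in the linear models and the daily creatinine model. State in advance how small centres will be pooled.

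**Appendix 3, Statistical analysis.** For every between-group comparison, including the 14-day one, use a linear model with group and site (three levels), and ideally the pre-transfusion value.

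The cost is one extra term per model and a pooling rule. No new data or patients are needed.

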This Renal substudy of the TRANSFUSE trial provides a unique opportunity to evaluate the effect of age of RBC on the incidence, severity and duration of AKI in critically ill patients and may also elucidate mechanisms involved in the body's response to RBC transfusion, thereby enhancing the parent study results. Leveraging the infrastructure and study design of the TRANSFUSE trial, this substudy provides a highly cost-efficient opportunity to test a clinically important hypothesis which cannot be answered outside such a large RCT and which would be unlikely to be funded as a separate study.

Methods

Renal function will be assessed in the TRANSFUSE trial using the KDIGO (Kidney Disease, Improving Global Outcomes) classification system[71] and an additional question at 90 day follow-up on the need for ongoing renal replacement therapy. There are no additional procedures required for this substudy.

Inclusion criteria: The same as for the TRANSFUSE trial. All patients recruited to the trial at Australian, New Zealand and other overseas sites that agree to participate in this substudy will be included.

Exclusion criteria: The same as for the TRANSFUSE trial with the following addition: patients with pre-existing end stage renal failure (receiving chronic dialysis) and those already undergoing renal replacement therapy at randomisation will be excluded.

Measurements

Renal function: AKI will be classified using the KDIGO classification system, the latest consensus classification system for AKI which has now been validated and used extensively[71, 72].

Ongoing renal replacement therapy: A question has been added to 90 day follow-up to ascertain whether the patient is receiving ongoing renal replacement therapy.

The only additional data to collect would be baseline creatinine defined as the most recent creatinine pre-randomisation, then the highest daily creatinine thereafter when available during the ICU stay for a maximum of 28 days (the duration of the trial follow-up in ICU). Collection of routine available creatinine values will be performed for this period, with no extra dedicated blood collection required for the substudy. The use of renal replacement therapy while in hospital will also be recorded as part of the TRANSFUSE parent trial.

Outcome measures

Primary outcome:

Cumulative proportion of patients with any degree of AKI

Secondary outcomes:

- a) The proportion of patients who develop stage 3 AKI (KDIGO criteria)

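### Renal substudy outcome (e): the plan does not say which term of the group-by-time model tests the 28-day mean creatinine, and the model as described leaves out the baseline value

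*Combined protocol and SAP*

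**What the plan says.** All of this is in Appendix 4 of the combined protocol and SAP.

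- Outcome measures, secondary outcome (e): "Comparison of the mean creatinine levels across the first 28 days".
- Measurements: the starting value is "baseline creatinine defined as the most recent creatinine pre-randomisation". The post-randomisation series is described as "then the highest daily creatinine thereafter when available during the ICU stay for a maximum of 28 days". Whether the baseline value enters the daily series as day 0 is not stated.
- Statistical Analysis, on daily values: "The difference between groups for daily serum creatinine will be determined using generalised linear modelling". The terms of that model are given as "fitting main effect for group and time and an interaction between group and time to determine if the two groups behave differently over time".
- Statistical Analysis, general methods: "Univariate analysis will be conducted using student t-tests, chi-square test for equal proportion or non-parametric tests where appropriate". For regression the section adds "Linear regression will be used for analysis of continuous outcomes". It also plans multivariable analysis adjusting for imbalances, covariates and confounders, none of them named.
- Statistical Analysis, significance: "A two-sided p-value of 0.05 will be considered to be statistically significant".

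The section does not say whether time is linear or categorical, where it starts, how the factors are coded, or which term or contrast is the test of (e). The only term given a stated purpose is the interaction.

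**The concern.** The null hypothesis of outcome (e) is that mean creatinine over the period is equal in the two arms. The interaction has a different null, that the two profiles are parallel. A difference that appears early and persists satisfies that null. Once an interaction is in the model, the meaning of the group coefficient depends on where time is zero and how the factors are coded. It can be the average difference, or it can be the difference at entry, which randomisation makes zero in expectation.

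The same sentence of the plan therefore allows analyses that answer different questions. The choice between them could be made after the data are seen. An analyst who reads both terms runs two tests for one outcome.

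**Working it through.** **The plan's own figure.** The substudy's power for any-stage AKI (19.5% v. 24.8%, 1000 per group, two-sided 0.05) reproduces: 81.5% without continuity correction, and n = 1000 per group for 80% power with it. No power is stated for creatinine.

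**What each term estimates.** Write the mean on day t as a + b1·group + b2·t + b3·group·t, with t in days from entry.

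- Between-group difference on day t: b1 + b3·t.
- Interaction: b3, the difference in slopes.
- Group term: b1, the difference at t = 0.
- Difference averaged over the days: b1 + b3·t̄, where t̄ is the (weighted) mean day.

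A constant shift has b3 = 0, so the interaction rejects at alpha. A difference growing linearly from zero has b1 = 0, so the entry-coded group term rejects at alpha. Neither result depends on the variances.

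**Effect of coding.** Take a true 28-day mean difference of 0.12 SD on days 1–28 (t̄ = 14.5).

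- Time centred at 14.5: the group term is b1 + b3·14.5, which is the average contrast itself.
- Categorical time, sum-to-zero coding: the group coefficient is 0.120 for both the constant and the linear profile.
- Categorical time, reference coding at day 1: 0.120 for the constant profile, but 0.12/14.5 = 0.008 for the linear one.

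**Illustrative power.** Assumptions, none from the documents: 1000 per group, complete days 1–28, mean difference 0.12 SD, correlation compound-symmetric or decaying by week, ρ from 0.5 to 0.9. Under compound symmetry the average contrast has variance (2/1000)·[ρ + (1 − ρ)/28].

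- ρ = 0.5: SE = √(0.002 × 0.5179) = 0.0322, ratio 0.12/0.0322 = 3.73, power Φ(3.73 − 1.96) = 96%.
- ρ = 0.9: SE = √(0.002 × 0.9036) = 0.0425, ratio 2.82, power 81%.

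Over all the correlations used:

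| True profile | Interaction | Group term, time from entry | Average contrast |
|---|---|---|---|
| Constant shift | 5% | 76–94% | 81–98% |
| Linear from zero | 96–100% | 5% | 81–98% |
| Crossing, mean difference zero | 97–100% | 78–96% | 5% |

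In the third row both fitted terms signal although the null of (e) is true.

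**Two tests for one outcome.** Two independent tests at 0.05 would reject at least once in 1 − 0.95² = 9.75% of null trials. Simulation of this model gave about 9%.

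**Baseline creatinine.** The simulation assumed log creatinine, 2000 patients, ICU stay averaging 8 days (maximum 28), patient-intercept SD 0.5, slope SD 0.02 per day, residual SD 0.2 and robust standard errors. The average contrast is the difference at the mean observed day.

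- Constant shift of 0.08: interaction 4.5–6% across runs; contrast 68–72% without baseline and about 99% with it.
- Divergence of 0.012 per day: entry-coded group term about 5%; contrast 78–79% without baseline and about 100% with it.

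The gain is large because between-patient level dominates the assumed variance. If the baseline value carries the same residual SD, it explains 0.25/(0.25 + 0.04) = 86% of the intercept variance, leaving 0.25 × 0.14 = 0.035.

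**Which days.** Under the assumed stay, the mean observed day is about 7, not 14.5. A divergence of 0.012 per day then averages 0.012 × 7 = 0.084 over observed patient-days, against 0.012 × 14.5 = 0.174 over 28 equally weighted days. The weights change the quantity being estimated.

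**The case against.** A reader might infer that neither term of the planned model tests the 28-day mean, so that the planned test is wrong. The documents do not support this. They fix neither the time origin nor the coding. A main effect of group can be read in the analysis-of-variance sense, averaged over time, and under that coding or with centred time it is exactly the test of (e). The wording about behaviour over time can also be read as giving the interaction only the question of shape. The t-tests and linear regression listed in the same section could be applied to a per-patient mean.

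A reader might also infer a power loss of 66 to 74 percentage points (70% v. 4.5%, and 78% v. 4.5%, in one simulation run). That compares the contrast with the mismatched term only. In that run the other fitted term did about as well: the group term rejected in 75% under the constant shift, and the interaction in 75% under divergence. In the analytic results, wherever one term fell to 5% the other had at least 76%. The plan fits both, so no such loss is shown for the plan.

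Two further points narrow the concern. If baseline is kept in the series as day 0, a pure constant shift is not expected under randomisation. And the general sentence on covariate adjustment could be taken to admit baseline creatinine.

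What remains is that no term is named as the test of (e). The general methods are not assigned to (e), so they add candidates without ranking them. Relying on whichever term is significant inflates the error rate. Baseline creatinine is not named in the daily-creatinine model or in the sentence on adjustment.

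**Conclusion.** The point holds as under-specification with a better method available at no cost. It does not show that the planned test is invalid. That the interaction does not test the mean difference, and that the group term does so only under some codings, follows from the model and needs no assumption. The 9% false-positive rate applies only if both terms are read without a rule.

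The power figures, including the gain from baseline adjustment, rest on assumed effect sizes, variances, correlations and ICU stay. They show direction and possible size and do not predict this trial's power. Outcome (e) is the last-listed secondary outcome of a substudy. The any-stage AKI endpoint and the 90-day mortality analysis are untouched. Severity is minor.

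**What to change.** Amend the Statistical Analysis section of Appendix 4 to say:

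- Outcome (e) is tested by one contrast from the daily-creatinine model: the between-group difference averaged over stated follow-up days with stated weights.
- The form of time, its origin and the factor coding are given.
- Pre-randomisation creatinine (on the log scale if the outcome is logged) is a covariate and not an outcome day.
- Values exist only during the ICU stay. The text should say whether the average is over observed ICU days or over all 28 days, and what the latter assumes about unobserved days.
- The group-by-time interaction is reported as a description of shape and does not decide whether the arms differ.

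This takes a few lines of text and one post-estimation contrast. It needs no new data, visits or patients.
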